The **Daily Tracking Group** will be given the traditional prescription of tracking every day during the 8-week intervention. The **1 On/1 Off Tracking Group** will be asked to track every day for a week, then to take a week off, and so on throughout the 8 weeks. This group will then track on weeks 1, 3, 5, and 7 for a total of 4 weeks of tracking. Although this group will only be tracking at the most 50% of the time, our previous study found that tracking 40% of the time was the threshold needed to lose ≥5% of weight which is the lower end of the program weight loss goal (5-10%). The **2 On/1 Off Tracking Group** will be asked to track every day for 2 weeks, then to take 1 week off, and so on throughout the 8 weeks. This group will then track on weeks 1, 2, 4, 5, 7, and 8, for a total of 6 weeks of tracking. Although this group will only be tracking at the most 67% of the time, our previous study found that tracking 67% of the time was the

threshold needed to lose ≥10% of weight which is the high end of the program weight loss goal (5-10%).

All three groups will be asked to continue their schedule of tracking in the month following the 8-week intervention (i.e., 12 weeks). We will compare groups on weight loss at 8 weeks, total days of tracking over 8 weeks, % who adhered to their prescription during the 8 week program, % who tracked <50% of the time, % who tracked >67% of the time, tracking burden, tracking enjoyment, intentions to continue tracking past 8 weeks, number of days tracked in the subsequent month, and weight loss at 12 weeks. Findings will inform a fully powered clinical trial of tracking prescriptions during a full-length weight loss program (6 months in duration).

Provide a clear and succinct summary description of the background information that led to the plan for this project:

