MyFitnessPal. All participants regardless of which group they are randomized into will be asked to use MyFitnessPal, the differences in the groups are the rate of which they track. Participants will be given a calorie goal based on their BMI, gender, age, and activity level to produce a weight loss of 1-2 lbs. per week. On days they are tracking, they will be asked to enter all the food and beverages they consume and their exercise with the purpose of staying under or at the calorie goal. Participants will use the free version of MyFitnessPal for this study.

Weigh-ins. Participants will receive a Wi-Fi scale mailed to them by the study team. This will allow them to take their weight weekly and at assessments. Weight is logged directly from the scale to an app designed for the scale. Using a Wi-Fi scale will allow for a standard weight measure for each participant with a higher level of accuracy than self-reported weight. Weight is logged directly from the scale to the participants' account. Participants will be asked to set up an account for the study and share login with the study staff so that the staff can record the weight taken. Study staff will help the participants set up their scale if they need it and check their BMI once the scale is working. If a participant has a BMI under 27, we exclude them from the study, and allow them to keep their scale as compensation. At the end of the study participants will be allowed to keep their scale and instructed to change their password. If they choose not to share their login for the duration of the study, they will be allowed to upload screenshots of their weight to a secure REDCap link. Study staff will delete the screenshot from REDCap once the weight has been logged into the record.

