Follow-ups/Assessments: The follow-ups/assessments will occur at the 9 and 12-week marks after the intervention has begun. At the 9-week mark (the week after the program ends), participants will receive a link to an online REDCap survey. This survey will be a repeat of some of the measures assessed at baseline (indicated in the measures table below) and questions to solicit participants' feedback. Then, at both the 9 and 12-week assessments, the participants will also weigh in. At the 12-week assessment, we will also collect their MFP diary entries, but that does not require the participant to do anything. Participants will be compensated (compensation explained in Payment/Course Credit to Participants section) for completing these assessments.

Adverse Events: Adverse events will be documented during the intervention and assessments. AE's will be formally assessed during the 9-week assessment by asking questions in the REDCap survey. During the intervention, AE's will be documented when a participant reports it to the

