weight loss counselor or posts it in the Facebook group. If it is reported during the intervention, the counselors will notify a research coordinator within 24 hours of learning of the event. The study team will then report it to the IRB (immediately or at the time of annual renewal depending on the AE). If participants gain 5% or more weight during the intervention, this will be treated as an adverse event. The participant will receive a phone call and/or email from a research coordinator, and they will be asked questions to figure out the cause of their weight gain. We will also assess Binge Eating Disorder (BED) at this time. If BED is present, we will treat it as a study-related AE. We will only assess BED once, even if there are multiple AEs for weight gain. Participants will not be removed from the intervention if they have 5% or more weight gain. If a participant is losing twice the weekly goal, which is 4 pounds of weight loss a week, consistently for 3 or more weeks in a row, then we will contact them to find out how they are accomplishing that and determine whether they are doing anything that is unsafe. If it is determined that they are losing weight in an unsafe manner, we will record that as an AE and the PI will have a discussion with them privately about healthy weight loss and how to do so in a safe manner moving forward. If after that conversation, they are still consistently losing 4 pounds of weight loss a week (for another 3 weeks or more in a row), we will remove them from the study and refer them to the National Eating Disorders Association helpline (https://www.nationaleatingdisorders.org/help-support/contact-helpline).

Measures: See table below.

Data Collected	List of Measures	Screening/	8-week	F/up	F/up	Method
		Baseline	Intervention	#1	#2	
Inclusion/Exclusion	Initial screening	Х				REDCap or
criteria	survey*					Qualtrics or
						BuildClinical
BMI	Height	X				REDCap
	Weight	X	X	Х	Χ	REDCap
Demographics	Marital status,	X				REDCap
	education,					
	race/ethnicity,					
	sexual orientation,					
	work status,					
	household income,					
	household					
	members*					
Nutrition Literacy	The Nutrition	X		Х		REDCap
	Literacy Assessment					
	Instrument (NLit) ²⁸					
History of Weight	Weight loss	X				REDCap
Loss	attempts*					

	Use of diet tracking* Use of diet tracking apps*					
Binge Eating	SCID Eating Disorder		X**	X**		REDCap
Disorder	Examination Questionnaire ³²					

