Nutritional Literacy. We will report on the % who are considered likelihood of poor nutrition literacy, possibility of poor nutrition literacy, and likelihood of good nutrition literacy. History of Weight loss attempts, diet tracking and diet tracking apps. Using descriptive statistics, we will summarize those who have a history of weight loss attempts, and use of diet tracking and diet tracking apps.

Amount of tracking. We will report the amount of tracking participants did throughout the intervention as well as one month following the intervention.

Contamination. We will report the percentage of participants that used any outside programs that provided weight loss coaching or another app to help with weight loss/exercise.

Burden. Using descriptive statistics, we will summarize burden scores in both treatment conditions. ANOVAs will be used to compare conditions on burden.

Weight loss. We will calculate weight change from baseline to 8 weeks as well as baseline to 12-weeks. As this pilot trial is not powered to detect differences, average changes will not be compared by treatment condition.

Inclusion/Exclusion Criteria

List ALL inclusion and exclusion criteria. Any proposed exclusion criterion based on gender (women of childbearing potential), age, or race must include rationale for the exclusion.

Inclusion Criteria

- 18-65 years old
- BMI 27-45 kg/m²
- Wi-Fi connectivity at home
- Logs into Facebook at least 5 days per week over the past 2 weeks
- Able to participate in the study in English
- Interested in losing weight
- Lives in US

Age justification: Children under 18 require different programming for weight loss and maintenance given their developmental needs. Weight loss is for elderly adults should be medically supervised, something this study is not offering.

Exclusion Criteria

- Pregnant/lactating or plans to become pregnant during study period
- Reports having bipolar disorder, substance abuse, psychosis, an eating disorder, or severe depression
- Had bariatric surgery or plans to have surgery during the study
- Currently taking medication affecting weight
- Has lost ≥5% of weight in past 3 months
- Is participating or intends to participate in another weight loss program during the study
- Chronic pain that interferes with the ability to exercise
- Type 1 Diabetes
- Type 2 Diabetes
- Unable to make dietary changes or increase physical activity
- Unable to walk ¼ mile unaided without stopping

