The data report for the 8-week intervention will be sent to the two safety officers once followups have been completed. Recruitment is monitored daily during the recruitment phase by the research coordinators and research assistants. All surveys are monitored once submitted to REDCap within 48 business hours by the research coordinators and research assistants. The Facebook group is monitored daily by the coaches. Weigh-in submissions are monitored weekly by the research coordinators and research assistants. App usage is monitored weekly by the research assistants, research coordinators, and the data managers. All data is continuously reviewed by the data managers.

2. Safety Monitoring Committee

The two safety officers for this project will include faculty independent from the research team with expertise in clinical psychology, exercise and weight loss interventions, and an understanding of the types and severity of injuries commonly experienced during weight loss trials. The two safety officers will review the reports sent by the PI/statistician and will use a checklist to document any corrective actions that should be communicated to the principal investigators, the University of Connecticut IRB, and the NIH. In addition, the safety officers may include documentation on whether the principal investigators should provide follow-up to a participant.

3. What data will be monitored:

Recruitment rates and adherence to inclusion/exclusion criteria, and ethnic diversity goals:

Recruitment progress, including baseline characteristics, will be reviewed. This review will ensure that project deadlines are being met, that participants meet eligibility criteria, and that the ethnic diversity goals outlined in the grant proposal are being met. Recruitment progress is monitored weekly, and a final report will be provided in the safety report.

Adherence to study protocols:

Quality control will be conducted in all phases of the project. The Facebook group will be monitored daily for intervention protocol adherence. A final report will be provided in the safety report.

Adverse events:

The adverse event report will include a listing of all adverse events including duration, severity, seriousness, relatedness, action taken, and resolution. Adverse events are documented throughout the intervention and at follow-up. A final AE report will be provided in the safety report. In the event of a serious adverse event, the safety officers will be notified immediately.

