Participant retention

Engagement will be tracked during the intervention, and completion of follow-ups will be documented. Participants will be reminded of upcoming study assessments. If a participant chooses to drop from the intervention, they will be given the option to skip the rest of the intervention, but still complete the follow-up. Retention is reviewed and discussed weekly throughout the study and at follow-up. A final retention and engagement report will be provided in the safety report.

Data review (completeness/outliers):

Reports will include completeness of data (visits completed, % of expected forms submitted, % of submitted forms passing edit); missed visits and missing information within visits; descriptive

information for each endpoint (change in weight and physical activity) without statistical testing; and quality control analyses for primary outcome (change in weight). Data will be cleaned at the end of each phase (screening, intervention, and follow-up). A final data review report will be provided in the safety report.

4. Data evaluated for problems

Data reports will be reviewed by the data manager, statistician, and PI.

5. Actions taken during certain occurrences

Baseline participants who report conditions that could create a safety concern while receiving the intervention will be excluded. Adverse events that occur during the intervention will be assessed, recorded, and followed up until resolved. Safety monitoring procedures will be documented in a standard protocol and overseen by the PI and program director. Any adverse events will be immediately reviewed by the program director. The safety officers will be informed of all adverse events during data review. Serious adverse events will be communicated immediately to the PI and safety officers. The NIH and UConn IRB will be notified immediately in the event of serious adverse event. Any death of a study participant will be reported to the NIH and UConn IRB whether or not it appears to be related to the study.

6. IRB Communications

The program director and research coordinator will communicate with the IRB. Communication will occur through emails, phone calls, and/or InfoEd as necessary.

7. Informing sponsor procedures

The sponsor will be notified within 48 hours of serious events that the IRB recommends we report.

Are there any plans to do an interim analysis? ⊠ No □ Yes
If yes, describe the interim analysis plan:

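### Weight change is planned as a two-point difference with its 8-week weight undefined, while the weekly study-scale weights already collected enter no outcome analysis

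*Protocol*

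**What the plan says.** All references are to the protocol.

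- **Status of the outcome.** Data Safety Monitoring, under Data review, refers to "quality control analyses for primary outcome (change in weight". No other section names a primary outcome.
- **Planned calculation.** The Weight loss item of Data Analysis reads "We will calculate weight change from baseline to 8 weeks as well as baseline to 12-weeks". It goes on: "As this pilot trial is not powered to detect differences, average changes will not be compared by treatment condition".
- **Assessment weigh-ins.** Follow-ups/Assessments places them one week after the program and one month after it: "Then, at both the 9 and 12-week assessments, the participants will also weigh in". No assessment weigh-in is set at week 8.
- **Weekly weights.** The Weigh-ins paragraph says of the mailed Wi-Fi scale: "This will allow them to take their weight weekly and at assessments". The measures table marks weight in the 8-week intervention column as well as at baseline and both follow-ups. Under Frequency of monitoring: "Weigh-in submissions are monitored weekly by the research coordinators and research assistants".
- **Stated uses of in-program weights.** They serve safety, for example "If participants gain 5% or more weight during the intervention, this will be treated as an adverse event", as well as the counselor's weekly weigh-in post and data monitoring. Nothing in Data Analysis draws on them.
- **A competing statement.** The Purpose/Introduction section says "We will compare groups on weight loss at 8 weeks, total days of tracking over 8 weeks", and its list ends with weight loss at 12 weeks.

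**The concern.** A difference between two weights can be formed only when both are present. Baseline is secure, because a study-scale weight is required before randomisation. The later weight is not: Removal from Study allows complete withdrawal, and Data Analysis expects to report retention by condition. If nothing is added to the stated calculation, each arm's mean describes those with an end-point weight and not all those assigned to the prescription.

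That matters if being missing goes with losing less. The background section reports steep falls in tracking over time and less weight loss in those who track less. It is plausible, though nowhere stated, that the same people more often fail to supply a weight. The means would then be too favourable. The Purpose/Introduction section says the findings will inform a fully powered trial, so an optimistic figure could enter its planning.

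The protocol already collects what would reduce the problem, namely repeated weights on the same device. The undefined 8-week value adds a second difficulty: two analysts could choose weights a week apart and both claim to follow the text.

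**Working it through.** **Reproducing the plan's figure.** The only sample-size figure is 108, justified by feasibility: 3 groups × 36 = 108. It reproduces. No attrition rate, SD or expected weight change is given, so every input below other than 36 per arm is an assumption.

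**Step 1: which weight is the 8-week weight?** Data Analysis says 8 weeks, Follow-ups/Assessments says week 9, and the measures table shows weights during the 8 program weeks. Both the last weekly weight and the week-9 weight fit the text, and no rule chooses between them.

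**Step 2: overstatement if those without the end-point weight are left out.** Let *a* be the share missing and *k* the absentees' mean loss as a fraction of the loss among those observed. The mean over everyone is (1 − a) + a·k times the observed mean, so the observed mean overstates it by

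1 / ((1 − a) + a·k) − 1.

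| Missing *a* | k = 0.5 | k = 0 |
|---|---|---|
| 10% | 1/0.95 − 1 = 5% | 1/0.90 − 1 = 11% |
| 20% | 1/0.90 − 1 = 11% | 1/0.80 − 1 = 25% |
| 30% | 1/0.85 − 1 = 18% | 1/0.70 − 1 = 43% |

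**Step 3: precision.** With 36 per arm, the 95% half-width for an arm mean is 1.96/√36 = 0.33 SD. With 10%, 20% and 30% missing, about 32, 29 and 25 remain. The half-widths become 0.35, 0.36 and 0.39 SD, and the standard error rises by 6%, 11% and 20%. Bias is the larger worry.

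**Step 4: would the weekly weights help?** A simulation used 3,000 runs with 36 in an arm. It assumed a mean slope of −0.35% per week (−3.15% at week 9), between-person SD 0.35% per week, weekly noise SD 0.7%, and dropout more likely in those who had lost less by week 3. The last column predicts missing week-9 values from the week-3 weight.

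| Missing | Everyone | Observed only (SE) | Using week-3 weight (SE) |
|---|---|---|---|
| 10% | −3.16% | −3.44% (0.57) | −3.17% (0.55) |
| 20% | −3.16% | −3.68% (0.60) | −3.16% (0.57) |
| 30% | −3.14% | −3.89% (0.64) | −3.14% (0.59) |

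Leaving absentees out overstates loss by about 0.3, 0.5 and 0.75 percentage points. One earlier weight removes this, but only because dropout was made to depend on a weight that everyone had supplied. The table shows what the method can do under that condition. It does not forecast this trial.

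**Step 5: if the arms were compared.** With equal true effects, k = 0.5, and 30% missing in one arm against 10% in another, the observed means would stand at 1/0.85 = 1.18 and 1/0.95 = 1.05 times the truth. Their ratio is 1.12, so dropout alone would create a gap of about 12%.

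**The case against.** The strongest reply is that the protocol never says participants without an end-point weight are excluded. It says only that change will be calculated. A mixed model also yields a change from baseline to 8 weeks, and missing-data handling is commonly left to an SAP, which is not shown here. This stands: exclusion is an inference from the stated calculation, and the lack of a missing-data rule is not itself an error. What remains is that the only method written down is a two-point difference, and that repeated weights on the same scale have no place in any outcome analysis.

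Second, the 8-week value may itself be a weekly weight, in which case the weekly series is not wholly unused. That also stands, and it is why the source must be named.

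Third, losses may be small. Weights pass from a home scale to an account normally shared with staff. There are payments of $50 and $25 for the two follow-ups, reminders, an orientation webinar meant to improve retention, and the option to leave the program but still be assessed. The background ties low tracking to less weight loss and says nothing about missed weigh-ins. All this limits the likely share missing but does not make it zero.

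Fourth, Data Analysis rules out comparing average changes by condition, so a reader who infers a biased treatment comparison goes beyond that section. The harm there is to descriptive estimates. The Purpose/Introduction section does promise a comparison, and only if that governs does Step 5 apply.

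Finally, people who disengage may stop weighing weekly too, and in-program weights are scheduled only within the 8 weeks. The gain at 12 weeks is therefore limited.

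**Conclusion.** The point holds in a limited form. The protocol reduces weight change to a two-point difference, leaves the 8-week weight undefined, and gives the weekly study-scale weights no role in estimating the outcome. A better estimate is available from data already being collected.

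The size cannot be fixed from the documents. If absentees lose half as much as those observed, the arm means overstate loss by 5% to 18% at 10% to 30% missing. If absence is unrelated to weight loss, there is no bias and only the loss of precision in Step 3.

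A reader might infer that the protocol excludes non-completers, that both end points rest on a single assessment weigh-in, or that in-program weights go unused. The first is not stated, the second is unsettled for 8 weeks, and the third is wrong for safety and monitoring. Nor do the documents say which of the pilot's numbers the later trial will use, only that its findings will inform that trial. The primary-outcome label itself rests on one mention in the monitoring section.

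This is a worthwhile, inexpensive improvement to a descriptive pilot analysis. It would matter more if the groups are in fact to be compared on weight loss.

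**What to change.** In the Weight loss item of Data Analysis:

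1. State which weight defines 8 weeks: the week-8 weekly weight or the week-9 assessment weight, with a window.
2. Replace the two-point difference with wording such as: *Mean weight change at that time and at 12 weeks will be estimated for each condition from a likelihood-based repeated-measures model using the baseline, all weekly and both follow-up study-scale weights of every randomised participant, with terms for time, condition, time by condition, and gender. Estimates will be given with 95% confidence intervals and without a between-condition test. The observed change, with its n, will be shown alongside.*
3. Name a simple covariance structure and a fallback. One weight per program week gives 1 + 8 + 2 = 11 occasions, and an unstructured matrix would need 11 × 12 / 2 = 66 parameters from 108 people.
4. Reconcile Purpose/Introduction, which compares groups on weight loss, with Data Analysis, which does not.

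The cost is a few sentences and a little more analysis, with no new data, visits or participants. The price in assumptions is that missingness must be explained by the weights already observed. For anyone who misses both follow-ups, the 12-week estimate still extrapolates beyond the program and the model adds little.
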